6.2. Safety Endpoints

6.2.1. Dose Limiting Toxicities [excluding the Expansion Cohort of LDAC Combination for Efficacy (Unfit Patient) and the Continuation Cohort]

The DLT evaluation of PF-04449913 is based on the definition in Protocol Section 3.2.

6.2.2. Adverse Events

Assessment of adverse events (AEs) will include the type, incidence, severity (graded by the National Cancer Institute Common Terminology Criteria for Adverse Events [NCI CTCAE] version 4.0) timing, seriousness, and relatedness. AEs will be coded using the Medical Dictionary for Regulatory Activities (MedDRA). AEs will be assigned to the appropriate cycle based on Day 1 of each cycle. Specifically, treatment emergent and treatment related AEs are defined as follows.

Treatment Emergent Adverse Events

- All deaths from start of treatment until 28 days after the final dose.
- All treatment related SAEs.
- All unrelated SAEs from treatment start until 28 days after final dose of treatment.
- All non-fatal AEs occurring after treatment start until 28 days after final dose of treatment.
- Disease progression is not considered a treatment emergent AE unless the subject dies of disease prior to 28 days after discontinuation of treatment.
- Events that are continuations of baseline abnormalities are considered treatment emergent AEs only if the grade increases from baseline.

Treatment Related Adverse Events

Treatment Related Adverse Events are AEs with cause categorized by the investigator as related to study treatment. Events that are continuations of baseline abnormalities (signs and symptoms) are not considered treatment emergent, and therefore not considered treatment related, unless there is an increase in grade over baseline.

6.2.3. Laboratory Safety Tests

Laboratory tests will be graded referring to CTCAE grade definitions. For laboratory tests without CTCAE grade definitions, results will be categorized as above, below, within or not done if the site has institutional ULN/LLN.

6.3. Other Endpoints

6.3.1. PK Endpoints (excluding the Continuation Cohort)

Monotherapy Cohort

Plasma PK parameters of PF-04449913.

The following single and multiple dose PK parameters will be calculated for PF-04449913 from the plasma concentration/time data obtained after PK Lead-In dose, on Day -5 (single dose) and Cycle 1 Day 21 (multiple dose), using non-compartmental method. Descriptive

statistics will be provided for these PK parameters in tabular form (n, mean, SD, CV, median, minimum, maximum, geometric mean and its associated CV) by dose, cycle and day.

- Single Dose - C_{max} , T_{max} , AUC_{last} , AUC_{τ} , CL/F , and V_z/F , $t_{1/2}$, AUC_{inf} as data permit.
- Multiple Dose (assuming steady-state is achieved) - C_{max} , T_{max} , AUC_{τ} , C_{min} , C_{av} , C_{trough} , CL/F , R_{ac} ($AUC_{ss,\tau}/AUC_{sd,\tau}$) and R_{ss} ($AUC_{ss,\tau}/AUC_{sd,inf}$) as data permit.

Combination Cohort 1 (Unfit Patients), Expansion Cohort of LDAC Combination for Efficacy (Unfit Patients), Cohort 2 (Fit Patients) and Cohort 3 (Azacitidine Combination)

Plasma PK parameters of PF-04449913, cytarabine, daunorubicin, and azacitidine.

Standard plasma PK parameters include C_{max} , T_{max} , and AUC for each drug (and metabolite if relevant) will be estimated using non-compartmental method. If data permit or if considered appropriate, C_{min} , C_{av} , C_{trough} , AUC_{inf} , and $t_{1/2}$ may be estimated. Descriptive statistics will be provided for these PK parameters in tabular form (n, mean, SD, CV, median, minimum, maximum, geometric mean and its associated CV) by analyte, dose, administration route, cycle and day.

For Expansion Cohort of LDAC combination for efficacy (Unfit Patients), descriptive summary of PF-04449913 concentration will be provided but PK parameters will not be calculated.

6.3.2. Drug-Drug Interaction Endpoints (Combination Cohorts Only)

6.3.2.1. Combination Cohort 1 (Unfit Patients): PF-04449913 and LDAC

The primary PK parameters, AUC and C_{max} , will be utilized to estimate the effect of coadministration of PF-04449913 and LDAC on the PK of either PF-04449913 or LDAC.

6.3.2.2. Combination Cohort 2 (Fit Patients): PF-04449913 and Cytarabine/Daunorubicin

The primary PK parameters, AUC and C_{max} , will be utilized to estimate the effect of coadministration of PF-04449913 and daunorubicin/cytarabine on the PK of PF-04449913.

6.3.2.3. Combination Cohort 3 (Azacitidine Combination): PF-04449913 and Azacitidine

The primary PK parameters, AUC and C_{max} , will be utilized to estimate the effect of co administration of PF-04449913 and azacitidine on the PK of either PF-04449913 or azacitidine.

6.3.3. ECG

Triplet, 12 lead ECGs for PF-04449913 is described in the relevant Schedule of Activities (see Protocol Table 1 through Table 6).

The baseline evaluations for ECGs are the average of the triplicate pre-dose values. The baseline ECG for Monotherapy Cohort and Combination Cohort 2 (Fit Patients) is defined as the last ECG(s) prior to the lead-in dose of PF-04449913. The baseline ECG for Combination Cohort 1 (Unfit Patients), Expansion Cohort of LDAC combination for efficacy (Unfit Patients), Combination Cohort 3 (Azacitidine Combination) is defined as the last ECG(s) prior to the dose of PF-04449913. If this was not collected, the baseline will be calculated from the ECG closest to the first dose of study drug during the screening period. If the last ECGs are triplicate ECGs (or only 2), they will be averaged. If the last ECG is a single, that will be used as baseline.

6.3.4. PD Biomarker Endpoints (excluding the Continuation Cohort)

PD Biomarker assessments may include the following; (i) evaluation of *Hh pathway genes and proteins*, (ii) circulating cytokine levels, and (iii) molecular analysis of somatic mutations and translocations with a known frequency of occurrence in the AML and MDS populations. Additional PD biomarkers may also be included, based on emerging data on *Hh pathway biology*.

The baseline PD biomarker measurements are defined to follow [Section 6](#).

6.3.5. Extramedullary Disease Endpoint (excluding the Continuation Cohort)

The baseline extramedullary disease assessments are defined to follow [Section 6](#).

6.4. Covariates

Not applicable.

7. HANDLING OF MISSING VALUES

7.1. Missing Dates

In compliance with Pfizer standards, if the day of the month is missing for any date used in a calculation, the 1st of the month will be used (unless for OS a later contact date in the month is established and then the day after will be used as the date of death for the patients with partial death date) to replace the missing date unless the calculation results in a negative time duration (eg, date of onset cannot be prior to day one date). In this case, the date resulting in duration of 1 day will be used. Pfizer standards are also used if both month and day are missing (Jan 1 unless negative time duration or for OS the day after the latest contact date in that year will be used as the date of death for the patients with partial death date).

7.2. Efficacy Analysis

For efficacy analyses, no values will be imputed for missing data. Censoring for time-to-event endpoints is defined in [Section 6.1](#).

In the assessment of CR/CRi or DMR rate, patients who are not known to have achieved the endpoint of interest (CR/CRi or DMR) will be counted as non-responders.

7.3. PK

Concentrations Below the Limit of Quantification

In all data presentations (except listings), concentrations below the limit of quantification (BLQ) will be set to zero. (In listings BLQ values will be reported as “<LLQ”, where LLQ will be replaced with the value for the lower limit of quantification).

Deviations, Missing Concentrations and Anomalous Values

In summary tables and plots of median profiles, statistics will be calculated with concentrations set to missing if one of the following cases is true:

1. A concentration has been reported as ND (ie, not done) or NS (ie, no sample),
2. A deviation in sampling time is of sufficient concern or a concentration has been flagged anomalous by the pharmacokineticist.

Note that summary statistics will not be presented at a particular time point if more than 50% of the data are missing.

PK Parameters

Actual PK sampling times will be used in the derivation of PK parameters.

If a PK parameter cannot be derived from a subject's concentration data, the parameter will be coded as NC (ie, not calculated). (Note that NC values will not be generated beyond the day that a subject discontinues).

For evaluation of changes in pharmacokinetics of a compound when administered alone vs. in combination, only subjects with matching pair of pharmacokinetic assessments under both conditions will be included in the pharmacokinetic summary (ie, alone and in combination).

In summary tables, statistics will not be presented for a particular treatment group if more than 50% of the data are NC. For statistical analyses (ie, analysis of variance), PK parameters coded as NC will also be set to missing.

If an individual subject has a known biased estimate of a PK parameter (due for example to an unexpected event such as vomiting before all the drug is absorbed in the body), this will be footnoted in summary tables and will not be included in the calculation of summary statistics or statistical analyses.

7.4. QTc

For analyses using the QTc-evaluable analysis set and safety analysis set, no values will be imputed for missing data except for averaging of triplicate measurements. If one or two of the triplicate measurements for an ECG parameter are missing, the average of the remaining two measurements or the single measurement can be used in the analyses. If all triplicate measurements are missing at a time point for an ECG parameter, no values will be imputed for this time point and this subject will be excluded from the analyses related to this time point. Unplanned ECGs will be in triplicate and averaged.

7.5. PD Parameters

Missing data for the pharmacodynamic parameters will be treated as such and no imputed values will be derived.

8. STATISTICAL METHODOLOGY AND STATISTICAL ANALYSES

8.1. Statistical Methods

Hypothesis testing will be performed as discussed in [Section 4](#).

8.1.1. Analyses of Time-to-Event Endpoints

Unless otherwise stated, time-to-event endpoints will be summarized using the Kaplan-Meier method and displayed graphically (with number of patients still at risk noted on the horizontal axis) when appropriate.

Median event times and two-sided 90% and 95% confidence intervals (CIs) for each time-to-event endpoint will be provided. Point estimate of selected survival probabilities and two-sided 90% and 95% CIs will also be provided, where the log-log transformation and back-transformation will be used in the calculation.

8.1.2. Analyses of Binary Endpoints

The rates of binary endpoints will be provided along with the corresponding two-sided 90% and 95% CIs using exact method.

8.1.3. Analyses of Continuous Data

The descriptive statistics, such as the mean, standard deviation, coefficient of variation, median, minimum, and maximum values, will be provided for continuous endpoints.

8.2. Statistical Analyses

For the Continuation Cohort, only the listings will be produced and the tables and figures will not be produced.

8.2.1. Analysis of Primary Endpoints

Monotherapy Cohort:

Analysis set: DLT-evaluable Analysis Set.

Table produced by: dose level.

Analysis:

The safety and tolerability is determined by quantification of patients experiencing DLTs at each dose level during the PK lead-in period and the first cycle of treatment.

Table: Number of patients who experienced DLT will be tabulated by dose level.

Listing: All records on DLT CRF page will be listed.

Combination Cohorts Other Than Expansion Cohort of LDAC combination for efficacy (Unfit Patients):

Analysis set: DLT-evaluable Analysis Set.

Table produced by: cohort (Combination Cohort 1, 2 and 3).

Analysis:

The safety and tolerability is determined by quantification of patients experiencing DLTs at each dose level during the PK lead-in period and the first cycle of treatment.

Table: Number of patients who experienced DLT will be tabulated by cohort.

Listing: All records on DLT CRF page will be listed.

Expansion Cohort of LDAC combination for efficacy (Unfit Patients):

Analysis set: Full Analysis Set.

Table produced by: Not applicable.

Analysis:

The DMR is defined in [Section 6.1](#). The number and percentage of patients who have ever achieved DMR will be summarized for irrespective of AML and MDS patients. An exact test for a single proportion (1-sided significance level: 0.05) will be used. The null hypothesis is that DMR rate=6.8%, and the alternative hypothesis is that DMR rate=34.1%. The two-sided 90% and 95% CIs will be also presented.

Table: Table will include the number and percentage of DMR responders, p-value and CI.

Listing: Not applicable. The listing of DMR will be included in the listing of disease response (see [Section 8.2.2.1](#)).

8.2.2. Analysis of Efficacy Endpoints

All efficacy analyses are secondary excluding the primary endpoint for Expansion Cohort of LDAC combination for efficacy (Unfit Patients) in the section above.

For Combination Cohort 1 (Unfit Patients), Expansion Cohort of LDAC combination for efficacy (Unfit Patients), and Combination Cohort 3 (Azacitidine Combination), the statistical analysis methods are described in the following sections.

For other cohorts, listings of subject's disease status on study will be provided by dose level, cohort and malignancy using the Full Analysis Set.

8.2.2.1. Disease Response

Combination Cohort 1 (Unfit Patients) and Expansion Cohort of LDAC combination for efficacy (Unfit Patients):

Analysis set: Full Analysis Set.

Table produced by: Table will be produced by cohort. See the following.

Analysis:

For AML patients, the best overall response will be summarized in frequency tables. The further endpoints of interest including CR/CRi and DMR will also be summarized with 90% and 95% exact CIs.

For MDS patients, the best overall response will be summarized in frequency tables. The further endpoints of interest including CR and DMR will also be summarized with 90% and 95% exact CIs.

For irrespective of AML and MDS patients, CR/CRi rate and DMR rate will be summarized in frequency tables with 90% and 95% exact CIs.

Table:

- Best overall response, CR/CRi and DMR for AML patients;
- Best overall response, CR and DMR for MDS patients;
- CR/CRi rate and DMR rate for irrespective of AML and MDS patients.

Listing: The disease responses will be listed by malignancy.

Combination Cohort 3 (Azacitidine Combination):

Same analyses described in Combination Cohort 1 (Unfit Patients) and Expansion Cohort of LDAC combination for efficacy (Unfit Patients) will be conducted. Note that only AML patients will be enrolled in this cohort.

8.2.2.2. Duration of Response

Combination Cohort 1 (Unfit Patients) and Expansion Cohort of LDAC combination for efficacy (Unfit Patients):

Analysis set: Full Analysis Set.

Table produced by: AML, MDS and irrespective of AML and MDS.

Analysis:

Kaplan-Meier estimates (productlimit estimates) will be presented together with a summary of associated statistics including the median duration of CR/CRi or DMR with two-sided 90% and 95% CIs.

Table:

- Summary of duration of response.

Figure:

- Kaplan-Meier curve of duration of response.

Listing:

- Listings include, but are not limited to, event/censor date, event/censor day from first dose, event type, reason for censoring, European Leukemia Net (ELN) cytogenetic risk and age (≤ 60 vs > 60 years).

Combination Cohort 3 (Azacitidine Combination):

Same analyses described in Combination Cohort 1 (Unfit Patients) and Expansion Cohort of LDAC combination for efficacy (Unfit Patients) will be conducted. Note that only AML patients will be enrolled in this cohort.

8.2.2.3. Time to Response

Combination Cohort 1 (Unfit Patients) and Expansion Cohort of LDAC combination for efficacy (Unfit Patients):

Analysis set: Full Analysis Set.

Table produced by: AML, MDS and irrespective of AML and MDS.

Analysis:

Kaplan-Meier estimates (productlimit estimates) will be presented together with a summary of associated statistics including the time to CR/CRi or DMR with two-sided 90% and 95% CIs.

Table:

- Summary of time to response.

Figure:

- Kaplan-Meier curve of time to response.

Listing:

- Listings include, but are not limited to, event/censor date, event/censor day from first dose, event type, reason for censoring, ELN cytogenetic risk and age (≤ 60 vs > 60 years).

Combination Cohort 3 (Azacitidine Combination):

Same analyses described in Combination Cohort 1 (Unfit Patients) and Expansion Cohort of LDAC combination for efficacy (Unfit Patients) will be conducted. Note that only AML patients will be enrolled in this cohort.

8.2.2.4. Overall Survival

Combination Cohort 1 (Unfit Patients) and Expansion Cohort of LDAC combination for efficacy (Unfit Patients):

Analysis set: Full Analysis Set.

Table produced by: AML, MDS and irrespective of AML and MDS.

Analysis:

OS time will be summarized using the Kaplan-Meier method (product-limit estimates) and displayed graphically where appropriate. CIs for the 25th, 50th, and 75th percentiles will be reported. In addition, the median OS and its two-sided 90% and 95% CIs using the Brookmeyer and Crowley method¹ will be provided.

The OS rate at 6, 12, and 18 months will be estimated with corresponding two-sided 90% and 95% CIs. The CIs for the median will be calculated according to Brookmeyer and Crowley and the CIs for the survival function estimates at the timepoints defined above will be derived using the log(-log) method according to Kalbfleisch and Prentice² (conftype=loglog default option in SAS Proc LIFETEST). The estimate of the standard error will be computed using Greenwood's formula.

Frequency (number and percentage) of patients with an event (death) and censoring reasons will be presented.

Table:

- Summary of OS.

Figure:

- Kaplan-Meier curve of OS.

Listing:

- Listings include, but are not limited to, event/censor date, event/censor day from first dose, event type, reason for censoring, ELN cytogenetic risk and age (≤ 60 vs > 60 years).

Combination Cohort 3 (Azacitidine Combination):

Same analyses described in Combination Cohort 1 (Unfit Patients) and Expansion Cohort of LDAC combination for efficacy (Unfit Patients) will be conducted. Note that only AML patients will be enrolled in this cohort.

8.2.2.5. Transfusions

Analysis set: Full Analysis Set.

Table produced by: AML, MDS, irrespective of AML and MDS for Combination Cohort 1 (Unfit Patients), Expansion Cohort of LDAC combination for efficacy (Unfit Patients), and Combination Cohort 3 (Azacitidine Combination), respectively.

Tables:

For the transfusion independence, the transfusion history and transfusion status on study will be summarized in frequency tables as following.

Mock Table:

Number (%) of Subjects		n++
Transfusion Status on Study		
Independent		n+1 (n+1/n++)
Dependent		n+2 (n+2/n++)
Not Followed for 8 Weeks		n+3 (n+3/n++)
Transfusion History		
Independent		n1+ (n1+/n++)
Transfusion Status on Study		
Independent		n11 (n11/n1+)
Dependent		n12 (n12/n1+)
Not Followed for 8 Weeks		n13 (n13/n1+)
Dependent		n2+ (n2+/n++)
Transfusion Status on Study		
Independent		n21 (n21/n2+)
Dependent		n22 (n22/n2+)
Not Followed for 8 Weeks		n23 (n23/n2+)

Notation:

Transfusion History	Transfusion Status on Study			Total
	Independent	Dependent	Not Followed for 8 Weeks	
Independent	n11	n12	n13	n1+
Dependent	n21	n22	n23	n2+
Total	n+1	n+2	n+3	n++
				(Full Analysis Set)

Listings:

- Transfusion records including transfusion type, date of transfusion and number of units (Listing by dose level, cohort);

- Transfusion independence: transfusion history and transfusion status on study.

8.2.3. Subset Analysis

Subset analyses will be performed for OS ([Section 8.2.2.4](#)) and transfusion independence ([Section 8.2.2.5](#)) based on the FAS for the subgroups defined below.

The following subgroups will be defined and used for analyses:

- DMR
 - DMR responder vs non-responder

Subset analyses for OS will use the primary censoring rules described in [Section 6.1](#). All the subgroup analyses are exploratory.

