6.1. Efficacy Endpoints (excluding the Continuation Cohort)

The efficacy endpoints of the disease response per investigator evaluation based on the Response Criteria CRF pages (see Protocol Appendix 5 through Appendix 9) is the primary method of documentation of disease. The response criteria differ for each hematologic malignancy (see [Appendix 2](#) through [Appendix 5](#) for details). Objective Response (OR) needs to be established before any subsequent documentation of progression.

The following dates are identified.

- The first objective response date: the assessment date of first documented objective response. However, these responses for MDS, CMML and CML need to be confirmed as described above.
- The first progression date: the assessment date of first documented (objective) disease progression.
- The first relapse date (except for CML): the assessment date of first documented relapse.
- The last disease assessment date: the date of last disease assessment date.

Combination Cohort 1 (Unfit Patients) and Expansion Cohort of LDAC combination for efficacy (Unfit Patients):

The following efficacy endpoints are defined.

DMR and its rate includes complete remission (CR), CR with incomplete blood count recovery (CRi), morphologic leukemia-free state (MLFS), marrow CR (mCR) and partial remission (PR) (see Protocol Appendix 5 and Appendix 8).

OS is defined as the time from the date of first dose of study drug to the date of death due to any cause. Patients last known to be alive will be censored at the date of last contact. The primary interest is the survival probability at 6 months and at 12 months.

Duration of response is only defined for patients who have ever achieved CR/CRi on study as the time from the date of first documentation of a CR/CRi (Protocol Appendix 5 and Appendix 8) to the date of loss of response after CR/CRi or death due to any cause. Duration of response data will be censored on the date of the last adequate response assessment for patients who do not have an event (loss of response or death). Duration of DMR for patients who have ever achieved DMR on study is also defined.

Time to response is only defined for patients who have ever achieved CR/CRi on study as the time from the date of first dose of study drug to the date of first documentation of a CR/CRi. Time to DMR for patients who have ever achieved DMR on study is also defined.

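### SAP 8.2.3 splits OS from first dose by later DMR status with no landmark or time-dependent method, so the split favours responders even if response does not affect survival

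*SAP*

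**What the plan says.** SAP 8.2.3 plans subset analyses of OS and of transfusion independence on the full analysis set. The one subgroup factor is DMR: "DMR responder vs non-responder". For OS it refers to SAP 8.2.2.4 and adds one rule: "Subset analyses for OS will use the primary censoring rules described in" SAP 6.1. It also says: "All the subgroup analyses are exploratory".

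SAP 6.1 fixes the time origin: "OS is defined as the time from the date of first dose of study drug to the date of death due to any cause". SAP 8.2.2.4 lists a Kaplan-Meier curve and the median with intervals, and adds: "The OS rate at 6, 12, and 18 months will be estimated".

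SAP 8.2.3 does not say who is a responder for this split. Two definitions stand elsewhere. The primary analysis in SAP 8.2.1 counts "patients who have ever achieved DMR". SAP 7.2, written for the response rates, says that "patients who are not known to have achieved the endpoint of interest (CR/CRi or DMR) will be counted as non-responders". Applying them to the OS split is an inference, but the documents offer no other definition.

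On-schedule marrows in the two LDAC cohorts start at Cycle 3 Day 1 and then follow at Cycles 6, 9 and 12 (Protocol Tables 2 and 3, footnote 19). In Combination Cohort 3 they start at Cycle 4 Day 1 (Protocol Table 5, footnote 15). In the LDAC cohorts a marrow after hematologic recovery, or one at the investigator's discretion, can date a response off this grid.

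**The concern.** DMR status is not known at first dose. It is acquired during follow-up, and only by patients who live long enough to have a response documented. With the clock starting at first dose, the responder group is credited with survival time that was guaranteed by the way the group was formed, and the earliest deaths collect in the other group. The two curves, the two medians and the 6-, 12- and 18-month rates would then differ without any link between response and survival.

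The usual remedies are a landmark or a time-dependent response status. Neither appears in the SAP or the protocol, and no caution accompanies the split. DMR is the primary endpoint of the Expansion Cohort, so survival curves by DMR status invite the reading that the endpoint predicts survival.

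**Working it through.** **The plan's own figure.** The documents give no number for the OS split. They do give the power of the DMR test. With 15 patients and success at 4 or more responders, the exact binomial gives P(X ≥ 4 | 0.341) = 0.808 and P(X ≥ 4 | 0.068) = 0.016. The stated 80.8% reproduces, and the OS split plays no part in that test.

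**Inputs.** Median OS 8.8 months and DMR rate p = 0.341 are the updated results of Study B1371003 for the combination (Protocol 1.2.8.1.3). Assessment days 57, 141 and 225 are Cycles 3, 6 and 9 Day 1 with 28-day cycles. Assumptions not in the documents: exponential survival, no effect of response on survival, no censoring, and the response timing of each scenario. A month is 30.4375 days.

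**Formulas.** Overall mean survival is m = 8.8 × 30.4375 / ln 2 = 386.4 days. Exponential survival has no memory, so a patient who responds at time t lives on average another m days. With mean response time T:
- responder mean R = m + T
- non-responder mean N = (m − p × R) / (1 − p)
- crude death-rate ratio, responder to non-responder = N / R

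**Worked case, responses at Cycles 3/6/9 in shares 50/30/20%.** T = 0.5 × 57 + 0.3 × 141 + 0.2 × 225 = 115.8 days. R = 386.4 + 115.8 = 502.2. N = (386.4 − 0.341 × 502.2) / 0.659 = 326.5. Ratio = 326.5 / 502.2 = 0.65.

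**All scenarios, with no true effect of response:**

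| Response timing | Death-rate ratio | Median OS, months (R vs N) | 12-month OS, % (R vs N) |
|---|---|---|---|
| All at day 28 | 0.90 | 9.7 vs 8.3 | 41.7 vs 37.4 |
| All at Cycle 3 Day 1 | 0.81 | 10.7 vs 7.7 | 45.0 vs 35.7 |
| Cycles 3/6/9, 50/30/20% | 0.65 | 12.8 vs 6.3 | 53.2 vs 31.5 |
| Constant chance at Cycles 3/6/9/12 | 0.59 | 13.8 vs 6.1 | 57.7 vs 29.0 |

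In the last row the chance per assessment is set at about 0.162, so that 34.1% ever respond. This gives T of about 142 days, R = 528.8 and N = 312.8. Whether time is counted as day 57 or as 56 elapsed days moves a ratio by no more than 0.003.

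**These rows are not limits.** Responses all at day 14, which a discretionary marrow would allow, give 0.95. Equal thirds at Cycles 3, 6 and 9 give 0.59.

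**Check of the remedies.** In simulations of these null scenarios, treating response as a time-dependent status gives a ratio of 1.00 to within simulation error. So does a day-64 landmark in the first three scenarios. In the last one, landmarks at Cycle 3 Day 1 and Cycle 6 Day 1 give equal medians (8.80 vs 8.78 and 8.81 vs 8.79 months).

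**What one trial of 15 would show.** The responder sample median is the higher one in about 60%, 69%, 86% and 91% of simulated trials for the four rows, against about 51% with no bias.

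**The case against.** The strongest reply is that little hangs on this split. The SAP calls it exploratory, plans no test or hazard ratio between the two groups, and uses it in no decision rule. With about 5 responders among 15 patients the intervals will be wide, and one cautionary sentence might suffice. Most of this stands, and it limits the weight of the point. But the exploratory label warns of imprecision and multiplicity, not of a bias with a known direction.

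It can also be said that the outputs are partly inferred. SAP 8.2.3 lists no tables or figures and names no cohort, and SAP 8.2.2.4 calls for graphs only where appropriate. That is fair for the two 6-patient cohorts. The reference to SAP 8.2.2.4 still makes its medians and rates the natural reading.

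A reader might go further in four ways that the documents do not support:
- That the trial's efficacy conclusion is compromised. The DMR test compares a proportion with 6.8% and does not use OS.
- That the SAP sets out to show that response prolongs survival. It plans no such claim.
- That the observed curves will favour responders. The bias is in expectation; a single data set can go either way.
- That the same reasoning removes the split from the 6-patient cohorts. That is a small-sample preference. The listings in Protocol 9.3 lend it little support, because SAP section 1 says that SAP version 4 supersedes the protocol's statistical sections and SAP 8.2.2.4 plans Kaplan-Meier summaries there.

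**Conclusion.** The point holds. The direction of the bias follows from the definitions: OS counts from first dose, responder status is acquired later, and deaths before a response are non-responders. It assumes only that the responder definitions of SAP 8.2.1 and 7.2 carry over to this split.

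The size cannot be fixed from the documents, because they give no response timing. Under the stated assumptions the null death-rate ratio is about 0.90, 0.81, 0.65 or 0.59 in the four timing patterns, with median gaps from 1.4 months (9.7 − 8.3) to 7.7 months (13.8 − 6.1). These illustrate the order of magnitude and do not bound it. The SAP should be changed because the change is cheap; the consequence of leaving it is a misleading exploratory display.

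**What to change.** In SAP 8.2.3, replace the OS split from first dose, including its medians and its 6-, 12- and 18-month rates, with one method fixed in advance:

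- **Simon-Makuch display.** Time runs from first dose. A patient counts as a non-responder until the date of first documented DMR and as a responder from that date, with numbers at risk shown.
- **Or a landmark at day 64 (Expansion Cohort).** Day 64 is Cycle 3 Day 1 (day 57) plus the 7-day marrow window. Include patients alive and in follow-up on that day, classify them by DMR documented by then, and count medians and rates from the landmark. Day 64 falls before the first scheduled on-treatment marrow of Combination Cohort 3, so it does not carry over there.

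For all cohorts add: *OS by DMR status is descriptive and does not estimate an effect of response on survival.* Where a 6-patient cohort has too few responders for a split, listing OS with the date of first DMR is an option, but it is not a correction of the bias.

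**Cost.** A few SAP lines and one re-programmed table and figure. No new data are needed, since SAP 6.1 already requires the date: "Time to DMR for patients who have ever achieved DMR on study is also defined".

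**Downsides.** The Simon-Makuch responder curve rests on about 5 patients (15 × 0.341 = 5.1) who enter late; in 0.6% to 7% of simulated 15-patient trials, over the first three timing patterns and an even mix of day 28 and Cycle 3 Day 1, it reaches zero before the last responder enters. The landmark drops early deaths, keeping 15 × exp(−64/386.4) = 12.7 patients on average, and counts later responders as non-responders. Over the same patterns it leaves 2.5 to 5.0 responders on average, with one or none in 26% to 2% of trials. Cycles may be extended (Protocol 5.3.9), so a delayed Cycle 3 marrow can fall after day 64. Neither method removes confounding by prognosis, which is why the added sentence is needed in either case.
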